3.2 General study level definitions

3.2.1 Analysis time points

3.2.1.1 Relative day

The relative day of a visit or an event with respect to the first application of study medication will be presented in subject data listings. Relative days will be calculated as follows:

- If the start (stop) date occurred prior to the first application of study medication, the relative day is calculated as start (stop) date minus date of first patch application. That means that in subject data listings, relative days based on this situation will be preceded by a ‘-’.
- If the start (stop) date occurred on or after the first application of study medication but prior to the last patch removal, the relative day is calculated as start (stop) date minus date of first patch application + 1.
- If the start (stop) date occurred after the date of last patch removal, the relative day is calculated as start (stop) date minus date of first patch application + 1. In subject data listings, relative days based on this situation will be preceded by a ‘+’.

Relative days will not be presented for partial or missing dates.

3.2.1.2 Date of last patch removal

The date of last patch application is documented on the Study Termination page of the eCRF. If the date of last patch application on this page is missing the last available kit start date on the Drug Accountability log form, with less patches returned than dispensed, will be used as the date of last patch application. Thus, the date of the last patch removal is defined as the date of the last patch application + 1.

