3.2.2 Study periods

The following time periods are defined for this study.

- Screening Period:

The Screening Period starts with Visit 1 and ends the day before the date of the first patch application.

- Titration Period:

The Titration Period starts at the day of the first patch application and ends the day before the date of Visit 5. In case of a premature withdrawal before Visit 5, the Titration Period ends at the day of the Withdrawal Visit. If the Withdrawal Visit is missing or the date of the last patch removal is before the Withdrawal Visit, the Titration Period ends at the day of last patch removal.

- Maintenance Period:

The Maintenance Period starts at Visit 5 and ends at Visit 9. If the subject withdraws prior to Visit 9, the Maintenance Period ends at the day of the Withdrawal Visit date or the last patch removal date (or last known patch removal date), whichever is earlier.

- Taper Period:

The Taper Period starts at the date of last maintenance patch removal and ends at the day of last patch removal. If the day of last patch removal is on the date of last maintenance patch removal, i.e., no de-escalation was performed for any reason, no Taper Period is defined for this subject.

- Treatment Period:

The Treatment Period comprises the Titration Period, the Maintenance Period, the Taper Period, i.e., it starts with the day of first patch application and ends on the maximum end date of the Titration, Maintenance and Taper periods.

- Safety Follow-Up Period:

The Safety Follow-Up Period starts the day after the end of the Treatment Period and ends at the date of the last study assessment. However, AEs starting within 30 days following the date of last patch removal will be included for analysis, even if the start date is after the date of last study assessment.

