10.2 Adverse events

Adverse events will be documented throughout the entire study on an ongoing basis. TEAEs are defined as events that started during the Treatment Period or within 30 days following the end of the Treatment Period (i.e., on or after the date of first patch application and within 30 days following the date of last patch removal) or any unresolved event already present before administration of treatment that worsens in intensity following exposure to the treatment. For AEs with a partial or missing start date, the imputation rules as described in [Section 4.2.2](#) will be applied.

Adverse events with a missing start date are defined as treatment-emergent if the end date of the AE is not on or before the date of first patch application.

An AE with action taken regarding study medication reported on the AE page of the eCRF as “drug permanently withdrawn” will be regarded as an AE leading to discontinuation of study medication.

Adverse events which have the question “Serious Adverse Event?” answered “yes” are considered serious.

Treatment emergent AEs will be tabulated by MedDRA SOC, High Level Term (HLT) and PT. The number and percentage of subjects experiencing each event at least once will be summarized in addition to the number of events. In summaries of TEAEs by relationship and intensity, respectively, the number of events will not be presented.

All summaries will be sorted alphabetically by SOC and HLT and by frequency of events (PT) within HLTs. If there is more than one PT with the same frequency these events will be sorted alphabetically.

An overview of the incidence and frequency of all TEAEs, serious TEAEs, TEAEs leading to discontinuation of study medication, related TEAEs, severe TEAEs, all deaths, and TEAEs leading to death will also be provided.

The following tabular summaries will be presented also.

- TEAEs
- TEAEs by intensity
- TEAEs by maximum intensity
- TEAEs by relationship to study medication per the Investigator
- Serious TEAEs
- Serious TEAEs by Relationship to study medication per the Investigator
- non-serious TEAEs above reporting frequency threshold of 5%

Individual subject data listings will be presented for all AEs.

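### When the last-patch date is missing, the SAP substitutes the start date of the last used kit and leaves out the patches worn from it, which is too early if kit start means first use

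*SAP*

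**What the plan says.** SAP 3.2.1.2 reads the last application date from the Study Termination page. If it is absent, the fallback points to a kit: "If the date of last patch application on this page is missing the last available kit start date on the Drug Accountability log form". The kit chosen is the latest one "with less patches returned than dispensed, will be used as the date of last patch application". The removal date is that date plus one day.

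The removal date is then used in several places:

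- **Exposure (SAP 10.1):** removal minus first application, plus one day. It is listed only.
- **Listing prefix (SAP 3.2.1.1):** "If the start (stop) date occurred after the date of last patch removal, the relative day is calculated" with a plus sign in front.
- **Study periods (SAP 3.2.2):** for a subject who withdraws before Visit 9, Maintenance "ends at the day of the Withdrawal Visit date or the last patch removal date (or last known patch removal date), whichever is earlier". The Treatment Period "ends on the maximum end date of the Titration, Maintenance and Taper periods".
- **TEAEs (SAP 10.2):** the window is given two ways and treated as one, "within 30 days following the end of the Treatment Period" and "within 30 days following the date of last patch removal".
- **Concomitant medication (SAP 6.4):** the window is the Treatment Period, described as closing on the day of last patch removal.
- **Efficacy (SAP 4.2.1):** an assessment more than one day after last patch removal is not used.

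**The concern.** A kit holds several patches (Protocol 7.6), and one is worn each 24 hours (Protocol 7.2.4). A kit's start date is therefore the date of its first patch at best, not its last. Choosing a kit because some patches were used, and then ignoring how many, gives a date that is right only if exactly one patch was worn.

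TEAEs are the primary safety variable, and an early removal date narrows their window. This runs against the SAP's other missing-data rules, which lean the cautious way: missing intensity counts as severe, missing relationship as related (SAP 4.2), and an event of undeterminable timing as treatment-emergent (SAP 4.2.2). The SAP also already uses a dated source, the eCRF drug dosing log (SAP 10.1), that this fallback does not consult.

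**Working it through.** The documents state no size for this error, so there is no figure to reproduce.

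**Inputs**

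- Removal = application + 1 (SAP 3.2.1.2).
- One patch per day (Protocol 7.2.4).
- Active taper patches in a full taper: 4, 2 and 0 for final doses of 3, 2 and 1 mg/24h (Protocol Table 7-3).
- Visit 9 falls 360 days after the start of Maintenance on Day 22 (SAP 3.2.3): 22 + 360 = Day 382.
- Assumed: kit start is the day of first use, with no replaced or missed patches. Kit size is not stated, so 7 and 28 are illustrations.

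**Error in the date.** Let the kit start on day s with g patches worn.

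- True last application: s + g - 1. True removal: s + g.
- SAP application: s. SAP removal: s + 1.
- Error: (s + g) - (s + 1) = g - 1 days early.

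| Last used kit | g | Days early |
|---|---|---|
| Separate taper kit, one patch worn | 1 | 0 |
| Separate taper kit, 2 mg/24h, full taper | 2 | 1 |
| Last of two taper kits (one per strength), 3 mg/24h, full taper | 2 | 1 |
| Separate taper kit, 3 mg/24h, three patches worn | 3 | 2 |
| Single separate taper kit, 3 mg/24h, full taper | 4 | 3 |
| Titration or maintenance kit, assumed size 7, all worn | 7 | 6 |
| Titration or maintenance kit, assumed size 28, all worn | 28 | 27 |

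The last two rows apply to anyone who did not taper and to every 1 mg/24h subject, who has no active taper patch. The protocol does not say whether taper patches form their own kit. Sections 8.3.4 and 8.4 also describe the taper shipment differently (available by Visit 9; part of the Visit 8 shipment) and should be reconciled.

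**Effect for a withdrawal**

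- Exposure: g - 1 days short.
- Plus-sign prefix: wrongly applied to dates s + 2 to s + g, which is g - 1 dates.
- Concomitant-medication window: g - 1 days short, with no 30-day buffer.
- TEAE window: closes on s + 31 instead of s + g + 30, so g - 1 days short. The part lost while still on patch is max(0, g - 31), which is 0 for g = 4, 7 or 28. A new-onset AE is lost only if it starts after day s + 31.
- Efficacy limit: s + 2. An assessment on the true removal day (s + g) fails once g is 3 or more; one on the last application day (s + g - 1) fails once g is 4 or more. A Withdrawal Visit held before a separate taper kit is opened stays valid.

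**Effect for a completer at 1 mg/24h** (true removal Day 382)

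- g = 7: kit starts Day 375, derived removal Day 376, error 382 - 376 = 6.
- g = 28: kit starts Day 354, derived removal Day 355, error 382 - 355 = 27.
- Exposure and the prefix carry that error, but Maintenance still ends at Visit 9. The TEAE window therefore closes on 382 + 30 = Day 412 if read from the end of the Treatment Period (no loss), or on Day 406 or Day 385 if read from last patch removal (6 or 27 days lost).

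**The case against.** The best case against acting is that very little depends on this. The rule operates only when the termination-page date is missing after data cleaning, and that may never happen. The study stopped early, the analyses are descriptive, exposure is only listed, and every AE is listed whether or not it is treatment-emergent. All of that stands and sets the severity.

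It is also fair that kit start is undefined here. If it is a dispensing date, the error differs from g - 1. It can even be late, for instance when an unworn kit is not returned and so counts as used. Same-day replacement of a detached patch (Protocol 7.2.6) reduces the error, and missed days increase it. The rule is therefore not always early.

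A reader might infer more than the documents support:

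- **A loss of about three months.** Treating the whole Visit 8 supply as one kit gives 89 to 93 days. For a 3 mg/24h subject that kit would have to hold three strengths. Protocol 8.1 speaks of several kit numbers for the Titration Period, and 8.2.2 has the kit returned at both Visit 3 and Visit 4. This points to several kits per shipment, though it does not prove it for Maintenance.
- **Completers losing Visit 9 efficacy data.** The one-day limit in SAP 4.2.1 follows a sentence about subjects who withdraw before the end of Maintenance and may be meant only for them.
- **Completers losing concomitant medications.** SAP 6.4 can be read as running to the end of the Treatment Period, which for completers is no earlier than Visit 9.
- **Loss of worsened events.** The TEAE definition also takes in "any unresolved event already present before administration of treatment that worsens in intensity following exposure to the treatment", with no stated end limit, so these are not clearly affected.

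Two possible rescues do not clearly work. The ambiguity rule in SAP 4.2.2 and the reference in SAP 3.2.2 to a last known removal date both help only when the date is unknown, and the fallback supplies a complete one.

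**Conclusion.** The point holds as a low-severity error in a stated rule. On its face SAP 3.2.1.2 omits the patches worn from the last used kit. If kit start means first use and patches are worn one a day, the derived date is g - 1 days early: 0 to 3 days with a separate taper kit, and usually more with a titration or maintenance kit (6 or 27 days under the assumed sizes). A maintenance kit opened just before stopping would still give a small error.

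Listed exposure and the plus-sign prefix are affected for everyone to whom the rule applies. The Treatment Period, the 30-day TEAE window and the efficacy limit are affected for withdrawals. The concomitant-medication window is affected where it is read as ending at last patch removal. A subject lost soon after opening a kit loses little or nothing. The formula is certain given its assumptions; the practical size is not, because kit size, the meaning of kit start and the number of missing dates are all unknown.

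**What to change.** In SAP 3.2.1.2, when the Study Termination date is missing:

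1. Use the last end date in the eCRF drug dosing log, stating whether it is an application or a removal date, since that decides whether the extra day is added.
2. If that is also missing, set last application = kit start + (dispensed - returned) - 1, with kit start defined as the day of first use, capped at the last contact or termination date. Check: 375 + 7 - 1 = Day 381, removal Day 382, as in the example.
3. If the return count is missing, use the cap date for TEAE and concomitant-medication classification only, and flag exposure as imputed.

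The cost is a few sentences and a small change to one derivation, with no new data. The dosing-log date may itself be missing, which is why steps 2 and 3 are needed. The downside is that lost, replaced or unreturned patches can make the date late, within the cap. That errs on the cautious side for TEAEs but can overstate listed exposure.

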3.2.2 Study periods

The following time periods are defined for this study.

- Screening Period:

The Screening Period starts with Visit 1 and ends the day before the date of the first patch application.

- Titration Period:

The Titration Period starts at the day of the first patch application and ends the day before the date of Visit 5. In case of a premature withdrawal before Visit 5, the Titration Period ends at the day of the Withdrawal Visit. If the Withdrawal Visit is missing or the date of the last patch removal is before the Withdrawal Visit, the Titration Period ends at the day of last patch removal.

- Maintenance Period:

The Maintenance Period starts at Visit 5 and ends at Visit 9. If the subject withdraws prior to Visit 9, the Maintenance Period ends at the day of the Withdrawal Visit date or the last patch removal date (or last known patch removal date), whichever is earlier.

- Taper Period:

The Taper Period starts at the date of last maintenance patch removal and ends at the day of last patch removal. If the day of last patch removal is on the date of last maintenance patch removal, i.e., no de-escalation was performed for any reason, no Taper Period is defined for this subject.

- Treatment Period:

The Treatment Period comprises the Titration Period, the Maintenance Period, the Taper Period, i.e., it starts with the day of first patch application and ends on the maximum end date of the Titration, Maintenance and Taper periods.

- Safety Follow-Up Period:

The Safety Follow-Up Period starts the day after the end of the Treatment Period and ends at the date of the last study assessment. However, AEs starting within 30 days following the date of last patch removal will be included for analysis, even if the start date is after the date of last study assessment.

3.2.3 Visit mapping

The visits are planned for the follow days:

Visit	Day	Visit Window
Visit 1 (Screening)	Day -4 to Day -1	
Visit 2, Day 1	Day 1	
Visit 3, Day 8	Day 8	± 3 Days
Visit 4, Day 15	Day 15	± 3 Days
Visit 5 (SoM)	Day 22 (or after reaching optimal dose)	± 3 Days
Visit 6 (Month 3)	90 Day after SoM	± 14 Days
Visit 7 (Month 6)	180 Day after SoM	± 14 Days
Visit 8 (Month 9)	270 Day after SoM	± 14 Days
Visit 9 (EoM)	360 Day after SoM	± 14 Days
Safety Follow-Up	30 Days after End of Taper Period	± 5 Days

During the Titration Period, the investigator should determine whether the subject has reached his/her final titrated dose level prior to completing the scheduled assessments for that visit. Subjects who have reached their final dose level should proceed to the Maintenance Period (Visit 5) and complete those assessments. Subjects who are back-titrated during the Titration Period will automatically enter the Maintenance Period.

Analysis by visit will be done as documented in the eCRF, i.e., no visit correction will be conducted due to deviations from scheduled time points.

Assessments at premature Withdrawal of the study are documented in the eCRF pages of Visit 9 (EoM/ Withdrawal). For data listings, assessments of Withdrawal Visit and of Visit 9 as scheduled will be presented separately as

- Premature Withdrawal for subjects who prematurely terminated the study
- Visit 9 (EoM) for subjects who completed the study.

Unscheduled assessments may be recorded during the study. Information collected in the log forms (e.g., AEs and concomitant medications) is included in the analysis. However, assessments at unscheduled visits will not be considered in the by visit analysis unless data captured at these visits falls within the SAP defined visit windows shown above and there was no corresponding endpoint data collected at the same scheduled visit. The information collected during unscheduled visits will be presented in the listings as an unscheduled visit.

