1 INTRODUCTION

This document contains details for the statistical analyses of study RL0007 supporting the clinical study report which has been written in consideration of the International Council for Harmonization (ICH)/Food and Drug Administration (FDA) E9 Guidance documents (Phillips et al, 2003). The reader is referred to the study protocol and the electronic Case Report form (eCRF) for details of study conduct and data collection.

The SAP describes the statistical principles that are applied for the analyses as well as tables and listings that are foreseen for this study. Changes in the statistical methodology result in a SAP amendment. Amendments to this document will be finalized prior to database lock.

This study was terminated early, and therefore the analysis described in this analysis plan is much more limited than that described in the protocol.

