4.2 Handling of dropouts or missing data

Subjects who prematurely discontinue the study will be evaluated based on the data collected at each visit attended. If the premature discontinuation occurs at a scheduled visit, data collected at that visit will be summarized at the scheduled visit time point. Otherwise, the data will be attributed to the next scheduled visit for the purpose of by-visit endpoint summaries.

With respect to AEs, events with missing intensity will be assumed to be severe. Events with missing relationship to study medication per the investigator will be assumed to be related. Events with a missing answer to the question “Serious Adverse Event?” will be considered serious.

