4.2.1 Missing efficacy data

For subjects who prematurely withdraw for any reason before EoM, values for planned efficacy assessments scheduled at subsequent visits will not be imputed. Efficacy assessments must be performed no later than 1 day after the last patch removal to be utilized for analysis (valid measurements).

For IRLS analysis if any item is missing, the IRLS sum score will be not calculated. Missing IRLS baseline value will be regarded as an important protocol deviation.

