8.1.2 Analysis of the key efficacy variables

Summary statistics for observed values as well as changes from Baseline by visit will be provided for IRLS sum score, each subscale of the RLS-6 rating scales and CGI item 1.

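### Does SAP 3.2.3 send every premature-withdrawal assessment to the Visit 9 summary row?

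*SAP*

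**What the plan says.** Three statements in SAP 3.2.3 (Visit mapping) bear on the point. First, "Analysis by visit will be done as documented in the eCRF, i.e., no visit correction will be conducted due to deviations from scheduled time points". Second, "Assessments at premature Withdrawal of the study are documented in the eCRF pages of Visit 9 (EoM/ Withdrawal" pages. Third, "For data listings, assessments of Withdrawal Visit and of Visit 9 as scheduled will be presented separately as" either Premature Withdrawal or Visit 9 (EoM). The section names no summary row for withdrawal data and does not refer to SAP 4.2.

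SAP 4.2 (Handling of dropouts or missing data) does name the row. For a subject who leaves at a planned visit, it says: "If the premature discontinuation occurs at a scheduled visit, data collected at that visit will be summarized at the scheduled visit time point". For a subject who leaves between planned visits, the rule is different: "Otherwise, the data will be attributed to the next scheduled visit for the purpose of by-visit endpoint summaries". SAP 4.2.1 adds that efficacy values at visits after withdrawal are not imputed, and it sets a validity limit: "Efficacy assessments must be performed no later than 1 day after the last patch removal to be utilized for analysis (valid measurements". Protocol 13.6 uses Withdrawal Visit data at the next planned visit.

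The by-visit tables survive the early stop. SAP 8.1.2 states that "Summary statistics for observed values as well as changes from Baseline by visit will be provided for IRLS sum score", for each RLS-6 subscale and for CGI Item 1. SAP 10.3 and 10.4.2 keep by-visit summaries of laboratory, endocrine and ECG data.

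**The concern.** A programmer usually takes visit assignment from the visit-mapping section. Taken alone, SAP 3.2.3 allows this chain: withdrawal data are on the Visit 9 pages, by-visit analysis follows the eCRF, and the separation applies to listings, so in summaries the data count as Visit 9.

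That row matters because the change from Baseline at Visit 9 in IRLS, CGI Item 1 and RLS-6 is the set of named secondary efficacy variables (Protocol 4.2.1, SAP 2.1.1.1). In a long-term follow-up study, mixing in values from the first weeks of Maintenance would blur what the Month 12 time point stands for. Early termination adds weight, since SAP 1 says "This study was terminated early, and therefore the analysis described in this analysis plan is much more limited than that described in the protocol", and assessments made before Month 12 on the shared pages may not be rare.

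There is also a loose end in SAP 4.2. Its next scheduled visit could mean (A) the next visit on the calendar or (B) the next visit at which that assessment is planned. The Withdrawal Visit uses the full Visit 9 battery (Protocol 8.6), so ECG, hormones and safety laboratory tests are taken whenever a subject leaves, including times near visits where none is planned.

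**Working it through.** The plan states no figure to reproduce. The check has a comparison of texts and a count of days.

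**Texts side by side**

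| Question | SAP 3.2.3 | SAP 4.2 |
|---|---|---|
| Where are withdrawal data recorded? | Shared Visit 9 (EoM/Withdrawal) pages | Not stated |
| How are they shown in listings? | Separately from Visit 9 | Not stated |
| Which row in by-visit summaries? | Not stated | Visit of discontinuation, otherwise next scheduled visit |
| Late or early scheduled visits? | No correction | Not stated |

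The two sections answer different questions. The no-correction sentence in 3.2.3 explains itself as being about deviations from planned timing. The eCRF page is shared by name, and 3.2.3 needs the two kinds of record told apart for listings, so they can be told apart for summaries too. Only 4.2 addresses the summary row.

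**Days on which a literal 3.2.3 would give a different row**

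Inputs: the visit days and windows in SAP 3.2.3, with Visit 5 (SoM) assumed on Day 22.

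- Study day = 22 + days after SoM: Visit 6 = 22 + 90 = 112; Visit 7 = 22 + 180 = 202; Visit 8 = 22 + 270 = 292; Visit 9 = 22 + 360 = 382.
- Windows of ±14 days: Visit 6, 98–126; Visit 7, 188–216; Visit 8, 278–306; Visit 9, 368–396.

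Under 4.2 with reading A, the days not sent to Visit 9 depend on what being at a scheduled visit means:

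- Exact planned day: Days 1–292, so 292/382 = 76%. The latest lies 368 − 292 = 76 days before the Visit 9 window opens.
- Inside the window: Days 1–306, so 306/382 = 80%. The gap is 368 − 306 = 62 days.

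On the Protocol Table 5-1 calendar (Visit 8 on D270, Visit 9 on D360), the exact-day figure is 270/360 = 75%.

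Example: a withdrawal 60 days after SoM goes to the Visit 6 row (day 90) under 4.2 and to the Visit 9 row (day 360) under the literal chain. The rows are 360 − 90 = 270 planned days apart.

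**Readings A and B of 4.2 during Maintenance**

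Planned visits from Protocol 8.2.3 to 8.3.4: efficacy scales at Visits 5 to 9; safety laboratory tests at Visits 5, 7 and 9; ECG and hormones at Visits 5 and 9.

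- Off-schedule days, exact-day basis: 4 gaps × 89 = 356.
- Off-schedule days, window basis: Days 26–97 (72), 127–187 (61), 217–277 (61) and 307–367 (61), total 255.

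| Assessment | A and B differ, exact day | A and B differ, window |
|---|---|---|
| Efficacy scales | 0 of 356 | 0 of 255 |
| Safety laboratory tests | 2 × 89 = 178 | 72 + 61 = 133 |
| ECG, hormones | 3 × 89 = 267 | 72 + 61 + 61 = 194 |

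Largest distance from the actual day to the labelled visit, exact-day basis:

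- A: 112 − 23 = 89.
- B: 202 − 23 = 179 for laboratory tests, and 382 − 23 = 359 for ECG and hormones.

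On the window basis:

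- A: 112 − 26 = 86.
- B: 202 − 26 = 176 for laboratory tests, and 382 − 26 = 356 for ECG and hormones.

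**The case for a change.** The strongest case for a change is that the ambiguity sits in the section programmers use for visit assignment, on the row that carries the secondary efficacy variables, in a study that stopped early. The two sections do not cite each other, and a sentence would cost almost nothing. The statements in SAP 4.2.1 and 8.1 that nothing is imputed do not settle it, because they concern missing later values and not the row for an observed withdrawal value. The one-day limit in 4.2.1 decides whether an efficacy value is valid, not where it goes.

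All of that is accurate as description. But the wrong outcome needs two errors together: stretching a sentence about visit timing to cover withdrawal data, and overlooking a rule written expressly for by-visit summaries. The day counts size that unlikely outcome. They do not show that the sections conflict, and as counts of days they say nothing about how many subjects are involved.

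The A/B question also stands as an open detail, and 4.2 alone does not close it for ECG, hormones and laboratory tests. Neither reading is clearly better, however. A keeps the label close in time but creates ECG and hormone rows at Visits 6 to 8, where none is planned. B avoids those rows but can place an early ECG or hormone value in the Visit 9 row. Asking for a statement of the choice would record a convention without improving the method.

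**Conclusion.** The concern does not call for a change. SAP 4.2 already fixes the summary row for withdrawal data. It agrees with Protocol 13.6 for exits between visits and adds the sensible rule that an exit at a scheduled visit stays there. What 3.2.3 lacks is a pointer, which a reader of the whole SAP supplies.

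If 3.2.3 were nonetheless programmed literally, the affected span would be 76% of planned days (exact-day basis) or 80% (window basis), assuming Visit 5 on Day 22. The number of subjects is not given. The consequence would be bounded: efficacy analyses are exploratory (Protocol 1) and descriptive, the primary safety variables are adverse-event counts that do not depend on visit rows, all data are listed (SAP 3.9), and listings mark premature withdrawals separately.

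The open detail in 4.2 makes no difference to the efficacy scales during Maintenance. For ECG, hormones and safety laboratory tests it affects only descriptive by-visit summaries of other safety variables, and analysts can settle it when the tables are specified.
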